5.1.3 Safety Analysis

Serious Adverse Event (SAE)

An event categorized as “Adverse Event” with the indicator flag “Serious” equal to “Yes” on the Events Case Report Form (eCRF) starting on or after signing of the informed consent and up to the End of Study date.

Treatment-emergent Adverse Event (TEAE)

An event categorized as “Adverse Event” on the Events eCRF starting on or after first dose of investigational product, as determined by “Did event start before first dose of investigational product” equal to “No” or missing, and up to the End of Study date.

Serious Treatment-emergent Adverse Events

A TEAE with the indicator flag “Serious” equal to “Yes” on the Events eCRF.

Treatment-emergent Adverse Device Effect

A TEAE with the indicator flag “Is there a reasonable possibility that the event may have been caused by the investigational device” equal to “Yes” on the Events eCRF.

Treatment-related Treatment-emergent Adverse Event

A treatment-emergent adverse event with the indicator flag “Is there a reasonable possibility that the event may have been caused by Investigational Medicinal Product” equal to “Yes” on the Events eCRF.

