9.4.2.3.1 Adverse Events

The Medical Dictionary for Regulatory Activities (MedDRA) will be used to code all adverse events.

Subject incidence of all treatment-emergent adverse events will be tabulated by system organ class and preferred term. Tables of fatal adverse events, serious adverse events, adverse events leading to discontinuation from investigational product and treatment-emergent adverse events of interest will also be provided. Subject incidence of device-related events, if applicable, will be tabulated by system organ class and preferred term.

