6.3 Safety Analysis Set

The safety analysis set (SAS) will consist of a subset of subjects from FAS who received at least 1 dose of investigational product. Analysis of safety endpoints and summary of investigational product administration will utilize the safety analysis set.

7. Planned Analyses

There is only one milestone analysis to be conducted for this study once **all the 240** enrolled subjects have completed the week 24/EOS visit. The data will be cleaned, and the database will be locked for the final analysis.

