9.6 Safety Analyses

All safety analyses will be performed based on all subjects in the Safety Analysis Set, both overall and separately by migraine prevention therapy standard of care status (continuation vs discontinuation).

The safety analysis will includes the adverse events, serious adverse events, and adverse device effects.

No formal hypothesis testing will be performed for this study.

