9.6.1 Adverse Events

The Medical Dictionary for Regulatory Activities (MedDRA) version **26.0** or later will be used to code all adverse events.

Subject incidence of all treatment-emergent adverse events will be tabulated by system organ class (SOC) and preferred term (PT). Tables of fatal adverse events, serious adverse events, adverse events leading to discontinuation from investigational product or other protocol-required therapies, and adverse events of interest (EOI) including:

- **Ischaemic Central Nervous System Vascular Conditions SMQ (Narrow)**
- **Ischaemic Heart Disease SMQ (Narrow and Broad)**
- **Peripheral Arterial Disease AMQ (Narrow)**
- **Hypertension SMQ (Narrow and Broad)**
- **Constipation AMQ (Narrow and Broad)**
- **Alopecias AMQ (Broad)**
- **COVID-19 SMQ (Narrow)**

Subject incidence of device-related events, if applicable, will be tabulated by system organ class and preferred term.

In addition, summaries of treatment-emergent and serious adverse events will be tabulated by SOC, PT, and grade.

The adverse event grading scale to be used for this study will be the Common Terminology Criteria for Adverse Events (CTCAE) version 4.03.

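### SAP 9.6.1 orders its serious-event tables with the term that SAP 5.1.3 defines from consent, so serious events before the first dose can be counted in the dosed population

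*SAP*

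**What the plan says.** SAP 5.1.3 sets up three terms that matter here:

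- A serious adverse event is a serious-flagged event "starting on or after signing of the informed consent and up to the End of Study date".
- A treatment-emergent adverse event is one "starting on or after first dose of investigational product" and up to the end of study.
- A serious treatment-emergent adverse event is "A TEAE with the indicator flag “Serious” equal to “Yes” on the Events eCRF", so it too runs only from the first dose.

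SAP 9.6.1 opens with a treatment-emergent table by system organ class and preferred term. It then lists "Tables of fatal adverse events, serious adverse events, adverse events leading to discontinuation from investigational product or other protocol-required therapies" and adverse events of interest, none of them with the treatment-emergent qualifier. It adds that "summaries of treatment-emergent and serious adverse events will be tabulated by SOC, PT, and grade".

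On the population, SAP 9.6 states: "All safety analyses will be performed based on all subjects in the Safety Analysis Set". SAP 6.3 defines that set as a "subset of subjects from FAS who received at least 1 dose of investigational product".

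The corresponding protocol section, 9.4.2.3.1, also names fatal and serious events without the qualifier, but says that tables of "treatment-emergent adverse events of interest will also be provided". SAP Section 10, which lists changes from the protocol-specified analyses, does not mention the dropped qualifier.

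**The concern.** The SAP keeps two serious-event definitions apart and then, where the tables are ordered, uses the name of the wider one. A programmer who follows the SAP's definitions would take the serious-event tables from consent onward. The population filter does not prevent this: it removes subjects who were never dosed, but not pre-dose events in subjects who were dosed later.

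The collection rules make the effect one-sided. Protocol 8.4.2.1.1 collects adverse events only after the first dose, whereas Protocol 8.4.2.1.2 collects serious events from consent. Pre-dose events in the database should therefore all be serious. A serious event could then appear in the serious-event table and be missing from the treatment-emergent table, so the two would not reconcile. Serious events of interest have the same problem once the qualifier is dropped.

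At stake is the serious-event incidence attributed to a population described as treated with erenumab. SAP 9.6 also splits the safety tables by whether standard-of-care prevention was continued or stopped. Under the protocol that choice is made after baseline, so a pre-dose event would be assigned to a group defined by something that happened later.

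**Working it through.** **1. Inputs**

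- Screening window: 0 to 21 days (Protocol 8.1.1).
- Baseline period: 28 to 35 days (Protocol 8.1.1).
- Treatment period: 24 weeks, 24 × 7 = 168 days (Protocol 4.1).
- Enrolled subjects: 240 (SAP 3.2), all taken as dosed.
- Serious-event rate: not given in either document, so it is assumed below.

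**2. The plan's own figure.** Protocol 4.4 gives a total duration per subject of about 28 to 32 weeks.

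- Shortest: (28 + 168)/7 = 28.0 weeks.
- Longest: (21 + 35 + 168)/7 = 32.0 weeks.

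Both ends reproduce, so the time from consent to day 1 is 28 to 56 days for a subject screened once. Protocol 8.1.1 requires consent to be repeated at rescreening only if rescreening begins more than 45 days after consent was signed. A rescreened subject could therefore have a longer window; that case is left out here.

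**3. Share of the counting window that lies before the first dose**

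- 28/(28 + 168) = 28/196 = 14.3%
- 56/(56 + 168) = 56/224 = 25.0%

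Relative to the treatment period alone, the consent-based window is longer by 28/168 = 16.7% to 56/168 = 33.3%.

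**4. Size in subjects.** Assume a constant hazard before and after the first dose, and a 24-week risk *r* of at least one serious event. With a pre-dose window of *d* days, the extra subjects in the table are

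240 × [(1 − r) − (1 − r)^((168 + d)/168)]

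| Assumed 24-week risk | d = 28 days | d = 56 days |
|---|---|---|
| 1% | 0.40 | 0.79 |
| 2% | 0.79 | 1.58 |
| 3% | 1.18 | 2.35 |
| 5% | 1.94 | 3.87 |

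For scale, a 1% risk means 2.4 subjects in the treatment period (240 × 0.01) and a 5% risk means 12 (240 × 0.05).

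**5. Which tables are affected**

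- *Serious events:* affected if the term in 9.6.1 carries its 5.1.3 meaning.
- *By grade:* unclear. The phrase can mean events that are both treatment-emergent and serious, or two sets of tables, one of which covers all serious events.
- *Events of interest:* affected for serious events only, and here the SAP differs from the protocol.
- *Fatal events:* hardly affected. A subject who dies before dosing cannot be in the Safety Analysis Set. Only an event that starts before dosing and leads to death after dosing could enter.
- *Main treatment-emergent table:* not affected.

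**The case against.** The best defence is that 9.6.1 cites neither definition. Its paragraph opens with treatment-emergent events, so the tables that follow can be read as subsets of those. The serious treatment-emergent definition has no evident use unless it is meant for these tables, which suggests that it may be the one intended. This stands as far as it goes: a reader might infer that the SAP lays down a settled rule putting pre-dose events into on-treatment tables, and the documents do not support that. They do not call these tables on-treatment, and the treatment-emergent reading is possible. But the SAP gives the unqualified term its own meaning, and that meaning starts at consent.

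Four other points stand:

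- Defining serious events from consent is not itself an error. It matches the collection period in Protocol 8.4.2.1.2.
- A reader might infer that the SAP departs from the protocol on serious and fatal events. It does not, because Protocol 9.4.2.3.1 also leaves those two unqualified. The departure concerns events of interest only, and may be a drafting slip in an incomplete sentence.
- The Events eCRF records whether an event began before the first dose, so the tables could be reconciled afterwards.
- The study is single-arm and descriptive, with no formal hypothesis testing of safety, so no comparison or decision rule depends on this.

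These points limit the consequence. They do not remove the need to say which definition each table uses.

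**Conclusion.** The point holds as a wording defect in SAP 9.6.1 that, on the SAP's own terms, gives the less suitable result: serious events between consent and day 1 in subjects later dosed would count in the Safety Analysis Set tables. The likely size is small, about 0.4 to 4 subjects of 240. That range rests on an assumed 24-week risk of 1% to 5%, a constant hazard, and all 240 subjects being dosed. Even so, one or two added subjects would be noticeable in a short serious-event table.

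A reader might take 25% as the most that pre-dose events could contribute. It is not a bound. It is the pre-dose share of calendar time when the rate is constant: a higher rate before dosing would exceed it, and failure of eligibility after a pre-dose serious event would lower it. A reader might also infer that deaths before the first dose enter the fatal-event table. The dosed-only population rules that out, apart from an event that begins before dosing and proves fatal afterwards.

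**What to change.** In SAP 9.6.1:

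- Order the serious-event tables and the by-grade serious tables with the serious treatment-emergent term already defined in 5.1.3.
- Restore the treatment-emergent qualifier to the events of interest, as in Protocol 9.4.2.3.1.
- List serious events from consent to first dose separately.
- Keep every on-study death in the fatal-event table and flag any whose event began before the first dose. Restricting that table to treatment-emergent events would drop such a death from it.

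The consent-based definition in 5.1.3 can stay, since it serves collection and the new listing. No new data are needed: whether an event began before the first dose is a mandatory attribute in Protocol Appendix 4 and already drives the treatment-emergent definition in SAP 5.1.3. The cost is SAP wording and one listing.

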5.2 Study Dates

Informed Consent Date

The date on which subject signs the informed consent form.

Date of Device Ready for Entry

The date on which an eDiary device is ready for data entry after completion of the eDiary training module.

Enrollment Date

Enrollment Date is the day a subject has met all eligibility criteria and is enrolled.

First IP Dose Date

First Dose Date is the date on which a subject is administered the first dose of IP following completion of the Baseline period as recorded on the IP Administration eCRF.

End of IP Administration Date

The end of IP admin date for each subject is defined as the date the decision was made to end IP as recorded on the End of IP eCRF.

End of Study (EOS) Date

End of study (EOS) date is defined as the last date on which the subject participates in the study as recorded on the End of Study eCRF.

5.3 Study Points of Reference

Baseline Assessment

Baseline assessment for the endpoint of the interest is defined as the last non-missing measurement taken or the monthly interval assessed (for endpoints derived from daily eDiary collection during baseline period) before the first dose of investigational product. In cases where baseline measurements are taken on the same day as IP, it will be assumed that these measurements are taken prior to IP being administered.

Study Day 1

Study Day 1 is defined as the first IP dose date **or enrollment date if no IP received**.

Study Day

Study Day is defined as the number of days from Study Day 1.

Before Study Day 1:

Study Day = (Date of Interest – Date of Study Day 1)

On or after Study Day 1:

Study Day = (Date of Interest – Date of Study Day 1) + 1

Therefore, the day prior to Study Day 1 is -1.

Treatment Discontinuation Visit

Treatment discontinuation visit is defined as the earliest visit on or after the date when the decision to discontinue treatment is made.

5.4 Study Time Intervals

5.4.1 Monthly Intervals for Efficacy Endpoints Derived From Daily Diary Collection

The (4-week) monthly intervals for efficacy endpoints derived from eDiary collection will be determined based on each subject's monthly IP dosing dates. When an IP is missed, discontinued, or no longer required, a 28-day monthly interval will be used.

Applicable efficacy endpoints utilizing the monthly intervals in [Table 5-2](#) includes:

- Monthly Migraine Days (MMD)
- Monthly Acute Migraine-specific Medication Days

Table 5-2. Monthly Intervals for Efficacy Endpoints Derived From Daily Diary Data Collection

Study Period	Assessment Timepoint	Monthly Interval	
		Start Date (Day) ^a	End Date (Day) ^b
Baseline Period	Baseline	Date of Device Ready for Entry	Day prior to study day 1
Open-label Treatment Period	Week 16 (Month 4)	Week 12 dose date	Week 16 dose date – 1
	Week 20 (Month 5)	Week 16 dose date	Week 20 dose date – 1
	Week 24 (Month 6)	Week 20 dose date	Week 24 visit date – 1

^a Start Date (Day) = End date (day) of previous monthly interval + 1 if IP dose date is not available

^b End Date (Day) = Start date (day) of current monthly interval + 27 if IP dose date is not available, unless stated otherwise

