7.1 Discontinuation of Study Treatment

Subjects can decline to continue receiving investigational product and/or procedures at any time during the study but continue participation in the study. If this occurs, the investigator is to discuss with the subject the appropriate processes for discontinuation from investigational product or procedures and must discuss with the subject the possibilities for continuation of the Schedule of Activities (see [Table 1-1](#)) including different options of follow-up (eg, in person, by phone/mail, through family/friends, in correspondence/communication with other treating physicians, from the review of medical records) and collection of data, including endpoints, adverse events, and device-related events and must document this decision in the subject's medical records. Subjects who have discontinued investigational product and/or procedures should not be automatically removed from the study. Whenever safe and feasible, it is imperative that subjects remain on-study to ensure safety surveillance and/or collection of outcome data.

Reasons for early removal from protocol-required investigational product(s) or procedural assessments may include any of the following:

- Decision by Sponsor
- Lost to follow-up
- Death
- Adverse event
- Lack of efficacy
- Subject request
- Ineligibility determined
- Protocol deviation
- Non-compliance
- Pregnancy

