5.1 Definition of Terms Included in Study Endpoints

5.1.1 Efficacy Endpoints Based on Monthly Collection

The daily eDiary collection will occur during the baseline period and months 4, 5, and 6.

Subjects' daily headache information will be collected through the following questions.

Possible outcomes on migraine-related endpoints are summarized below:

Table 5-1. Definitions of Migraine Day, Headache Day, and Acute Migraine-specific Medication Day

	Scenarios									
	1	2	3	4	5	6	7	8	9	10
eDiary data collection										
Headache (Y/N)	Yes	Yes	Yes	Yes	Yes	Yes	No	No	No	No
If Y, (a) Pain intensity (1 to 10)	1 to 10	1 to 10	1 to 10	1 to 10	1 to 10	1 to 10	NA	NA	NA	NA
(b) Migraine (Y/N)	Yes	Yes	Yes	No	No	No	NA	NA	NA	NA
(c) Acute medication for headache (Y/N)	Yes	Yes	No	Yes	Yes	No	NA	NA	NA	NA
If Y, Triptan (Y/N)	Yes	No	NA	Yes	No	NA	NA	NA	NA	NA
If N, Aura (Y/N)	NA	NA	NA	NA	NA	NA	Yes	Yes	Yes	No
If Y, acute medication for aura (Y/N)	NA	NA	NA	NA	NA	NA	Yes	Yes	No	NA
If Y, Triptan (Y/N)	NA	NA	NA	NA	NA	NA	Yes	No	NA	NA
Endpoint definition										
Headache Day	Yes	Yes	Yes	Yes	Yes	Yes	Yes	No	No	No
Migraine Day	Yes	Yes	Yes	Yes	No	No	Yes	No	No	No
Acute Migraine-specific Medication Day	Yes	No	No	Yes	No	No	Yes	No	No	No

Migraine Type

CM is defined as subjects with ≥ 15 headache days per month of which ≥ 8 headache days meet criteria as migraine on either CRF data collected on form “Headache and Migraine Frequency Medical History” during screening or eDiary collection during baseline; **EM** is defined as subjects who does not fulfill criteria for **CM**.

Diary Day

A calendar day (00:00 to 23:59) with complete migraine headache, aura, and acute migraine headache medication data recorded in the eDiary device

Headache Day

A calendar day (00:00 to 23:59) in which the subject reports a headache (ie, Scenarios 1 to 7 in [Table 5-1](#))

Migraine Day

A calendar day (00:00 to 23:59) in which the subject reports a migraine (ie, Scenarios 1 to 4 in [Table 5-1](#)) or takes a migraine-specific medication (ie, Scenario 7 in [Table 5-1](#))

Acute Migraine-specific Medication Day

A calendar day (00:00 to 23:59) in which the subject takes a migraine-specific medication (ie, Scenarios 1, 4, and 7 in [Table 5-1](#)).

Monthly Frequency Variable in Days

Number of days of interest during one monthly interval as defined in [Table 5-2](#). Monthly frequency variables include

- Monthly Migraine Days (MMD)
- Monthly Acute Migraine-specific Medication Days

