8.3 Handling of Missing and Incomplete Data

Subjects may miss specific data points for a variety of causes. In general, data could be missing due to a subject's early withdrawal from study, a missed visit, inability to evaluate an endpoint at a particular point in time, and treatment discontinuation due to lack of efficacy, adverse event, or non-response. The efficacy endpoints will be collected via daily eDiary and monthly eCOA assessments device. Subjects could miss entering several days of daily migraine data or an eCOA assessment in each monthly interval.

The general procedures outlined below describe how missing data will be handled.

For the eDiary data collected daily, if at least 14 days of eDiary are collected in the monthly interval, then the monthly frequency measurements (eg, headache days, migraine days or acute migraine-specific medications days [AMSMD]) will be prorated based on the number of days with available information. If less than 14 days of eDiary are collected in the monthly interval, then the monthly frequency measurements will be set to missing ([Table 8-1](#)). For the descriptive summary of the mean monthly value calculated using the monthly value from each of months 4, 5, and 6, if a subject has at least one monthly value at months 4, 5, and 6, then the subject contributes to the summary statistics.

For the endpoints derived from the daily diary data, please refer to proration approach specified in [Section 5.1.1](#). On handling missing daily diary data. Missing monthly measurement after proration will be handled by statistical analysis approaches listed in [Section 9.5](#).

Table 8-1. Handling of Missing and Incomplete eDiary Data

Monthly Frequency Endpoint	Condition	Proration Method (Without Rounding)
Monthly frequency measurements (migraine days and acute migraine-specific medication days)	
A diary day is a day with all headache-related questions completed in eDiary.
 
If diary days in baseline or each post-baseline interval ≥ 14, apply proration for that monthly interval;
 
Else monthly frequency measurement is set to missing
	
Number of event days of interest in a monthly interval* 28/ Number of diary days in the monthly interval
 
Note: Event days of interest is referred to migraine days and acute migraine-specific medication days

Missing or incomplete dates will be listed as reported, except for incomplete start date of an adverse event or concomitant medication ([Table 8-2](#)).

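### SAP Table 5-2 does not say where diary month 4 starts for a subject who stops erenumab before week 12; read literally, it starts at study day 1, when no diary is kept

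*SAP*

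**What the plan says.** Table 5-2 in SAP 5.4.1 defines four diary intervals: baseline and months 4, 5 and 6. Baseline ends on the "Day prior to study day 1". Months 4, 5 and 6 start at the week 12, 16 and 20 doses. Months 4 and 5 end the day before the next dose, and month 6 ends on "Week 24 visit date – 1".

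Two footnotes cover absent dose dates. The start becomes "End date (day) of previous monthly interval + 1 if IP dose date is not available", and the end becomes "Start date (day) of current monthly interval + 27 if IP dose date is not available, unless stated otherwise". The text above the table adds: "When an IP is missed, discontinued, or no longer required, a 28-day monthly interval will be used".

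SAP 5.1.1 states when the diary is kept: "The daily eDiary collection will occur during the baseline period and months 4, 5, and 6". SAP 8.3 sets the minimum: "If less than 14 days of eDiary are collected in the monthly interval, then the monthly frequency measurements will be set to missing".

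Subjects who stop treatment are meant to be followed and analysed. Protocol 7.1 says that, where safe and feasible, "it is imperative that subjects remain on-study". SAP 9.1 analyses exploratory endpoints as observed, with no adjustment for stopping treatment. SAP 6.2 requires only one dose for the efficacy set. SAP 9.5 defines the dose covariate even for a subject who received none of the three doses from week 12 to week 20.

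**The concern.** The fallback in footnote a needs a previous interval. For months 5 and 6 one exists. For month 4 the row above is baseline, and SAP 5.3 itself treats the diary baseline as a monthly interval, so the literal reading is not far-fetched. It attaches the label week 16 (month 4) to the first four weeks of treatment, before diary collection resumes. The 28-day sentence gives a length but no start day, so it does not close the gap.

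At stake are the by-month diary results of subjects who stop before week 12 and go on recording: change in MMD, 50% response and acute migraine-specific medication days at weeks 16, 20 and 24. Under one reading of month 6, the mean over months 4 to 6 is lost as well. Two competent programmers could obtain different datasets from the same text.

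**Working it through.** **Inputs**
- Day numbering (SAP 5.3): day 1 is the first dose and the day before it is day -1, so the day after baseline ends is day 1.
- Target day for week w = 1 + 7w. Weeks 12, 16, 20 and 24 give 85, 113, 141 and 169, which reproduces the target days in SAP Tables 5-3 to 5-6.
- Diary on schedule (SAP 5.1.1, months 4 to 6): days 85 to 168, which is 84 days.
- Proration (SAP 5.1.1): event days / diary days × 28 if there are at least 14 diary days, otherwise missing.

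**Step 1. All doses on schedule.** Month 4 is days 85-112, month 5 days 113-140 and month 6 days 141-168, each with 28 diary days. The table works as intended.

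**Step 2. No dose from week 12 onward, footnotes read literally.** Month 4 starts on day 1 and ends on 1 + 27 = 28. Month 5 starts on day 29 and ends on 29 + 27 = 56. Month 6 starts on day 57. Its end can be read in two ways:
- Reading A: the week 24 visit date is available, so month 6 ends on 169 - 1 = 168.
- Reading B: footnote b or the 28-day sentence governs, so month 6 ends on 57 + 27 = 84.

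| Interval | Days | Length | Diary days | Result |
|---|---|---|---|---|
| Month 4 | 1-28 | 28 | 0 | missing |
| Month 5 | 29-56 | 28 | 0 | missing |
| Month 6, reading A | 57-168 | 112 | 84 | prorated |
| Month 6, reading B | 57-84 | 28 | 0 | missing |

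**Step 3. What reading A reports as month 6.** It is the average of the three true months. Suppose (assumed counts) that a subject with a complete diary has 10, 8 and 6 migraine days in months 4, 5 and 6. The result is (10 + 8 + 6) / 84 × 28 = 8.0, where the true month 6 value is 6. With 6, 8 and 10 the result is again 8.0, where the true value is 10. The error can go either way. The mean over months 4 to 6 then rests on this single value, which SAP 8.3 allows for the descriptive mean. In both examples it equals the true mean of 8.

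**Step 4. Visit timing.** The protocol allows visits within 7 days of schedule. With the diary starting on day 78, 85 or 92, months 4 and 5 still hold 0 diary days. Days 57-84 hold at most 7 (days 78-84), which is below 14.

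**Step 5. Chained reading.** If unlisted months 1 to 3 are built as 28-day intervals from day 1, month 3 ends on day 3 × 28 = 84 and month 4 starts on day 85. The windows are then days 85-112, 113-140 and 141-168 with 28 diary days each, and nothing is lost.

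**Step 6. Who is not affected.** A subject whose last dose is at week 12 has the start date and gets the windows of step 1. A subject who misses only the week 12 dose and is dosed at week 16 gets a literal month 4 of days 1-112. It holds only the 28 diary days 85-112, so proration returns the right value.

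**The case against.** The strongest reply is that the literal reading is not what was meant. The rows are numbered months 4, 5 and 6, so the interval before month 4 is naturally month 3. Four-week steps from day 1 reach day 85, the week 12 target day elsewhere in the SAP. Placing month 4 on days 1-28 contradicts the row's own label and the statement of when the diary is kept. A sensible programmer would probably notice.

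This has force as a guess at intent, and it means that the literal result cannot be called the plan's certain outcome. It does not remove the gap. Months 1 to 3 have no rows, no dates and no diary, and nothing in the SAP says to construct them.

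A reader might also infer that the rule discards all diary data from early stoppers. That holds only under reading B. Reading A keeps all 84 diary days, and the mean over months 4 to 6 is about right when the diary is complete. Reading A does, however, produce a 112-day interval, which conflicts with the SAP's own 28-day sentence.

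**Conclusion.** The SAP leaves the start of month 4 undefined for a subject without a week 12 dose, and its literal fallback gives a wrong answer for those who have stopped. The by-month diary values are wrong or missing under both literal readings. The mean over months 4 to 6, and the 50% response based on it, are lost only under reading B. The point rests on the subject stopping before week 12, staying on study and completing enough diary in months 4 to 6.

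The reach is narrow. The primary satisfaction score and all secondary endpoints use the visit windows of Tables 5-3, 5-4 and 5-6, and baseline MMD has its own row in Table 5-2. The study is descriptive, with no formal hypothesis. This is a minor point, worth correcting because it costs almost nothing.

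The documents do not support two further inferences:
- **Bias in favour of erenumab.** This would require the omitted subjects to do worse than the rest. The documents give no data on that, those who stop for other reasons need not do worse, and step 3 shows that the month 6 error can take either sign.
- **A count of affected subjects.** The 10% dropout in SAP 3.2 is loss by week 24. It is not the share who stop before week 12 and keep the diary, so it cannot be applied to the 240 enrolled.

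**What to change.** Add one sentence to footnote a of Table 5-2: *If there is no week 12 dose date, month 4 starts on the week 12 visit date, or on study day 85 if there was no visit; months 5 and 6 use later dose dates where available, otherwise consecutive 28-day intervals.*

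The last clause matters. Without it, the anchor would override the real week 16 and week 20 dose dates of a subject who only missed the week 12 dose. For a subject who has stopped, the clause also settles the length of month 6 in line with the 28-day sentence. With the day 85 anchor, the windows for a subject who has stopped are days 85-112, 113-140 and 141-168, each with 28 diary days if the diary is complete.

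The cost is one sentence in the SAP and a small change in the derivation program. No new data are needed, and subjects with a week 12 dose date keep their current windows.
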